**Protocol for non-interventional studies based on existing data:**

Document Number:	c12696196-01
BI Study Number:	1160.219
BI Investigational Product(s):	PRADAXA (dabigatran)
Title:	Validation of predictors for oral anticoagulant medication choice using EMR data (Phase 3b of the BI/BWH Pradaxa study program)
Protocol version identifier:	1.0
Date of last version of protocol:	02 November 2016
PASS:	No
EU PAS register number:	Not available yet
Active substance:	Dabigatran etexilate
Medicinal product:	Pradaxa
Product reference:	EU/1/08/442/001-019
Procedure number:	EMEA/H/C/000829
Joint PASS:	Not applicable
Research question and objectives:	
The research question is whether select patient characteristics that may be incompletely captured by insurance claims data, differ between dabigatran and warfarin initiators.
 
Objectives:
 
 
1) Descriptive: To identify select clinical covariates from electronic medical records that might be associated with initiation of oral anticoagulant medications (dabigatran or warfarin) in NVAF patients at risk for stroke and are not usually well captured in the associated claims database
 
2) Prediction Rule: To assess how well EMR-based clinical characteristics can be captured on the basis of claims data only
 
3) Assess Balance: To assess the potential for unmeasured confounding in dabigatran vs warfarin comparative effectiveness and safety studies based on administrative claims
 

Proprietary confidential information © 2016 Boehringer Ingelheim International GmbH or one or more of its affiliated companies

	databases
Country(-ies) of study:	US
Author:	
Marketing authorisation holder(s):	Boehringer Ingelheim
MAH contact person:	
Date:	02 November 2016
Page 2 of 55	
Proprietary confidential information © 2016 Boehringer Ingelheim International GmbH or one or more of its affiliated companies. All rights reserved. This document may not - in full or in part - be passed on, reproduced, published or otherwise used without prior written permission	

## 2. LIST OF ABBREVIATIONS

ACCP	American College of Chest Physicians
ACEI	Angiotensin-converting Enzyme Inhibitor
AES	Advanced Encryption Standard
AF	Atrial Fibrillation
ALT	Serum Alanine Aminotransferase
ARB	Angiotensin Receptor Blocker
ASCVD	Atherosclerotic Cardiovascular Disease
BB	Beta Blocker
BI	Boehringer Ingelheim
BMI	Body Mass Index
BWH	Brigham and Women's Hospital
CABG	Coronary Artery Bypass Graft
CAD	Coronary Artery Disease
CCB	Calcium Channel Blocker
CHA 2 DS 2 -VASc	Congestive Heart Failure, Hypertension, Age > 75, Diabetes Mellitus, Prior Stroke or Transient Ischemic Attack, Vascular Disease, Age 65-74, Sex Category
CHADS 2	Congestive Heart Failure, Hypertension, Age > 75, Diabetes Mellitus, Prior Stroke or Transient Ischemic Attack
CHF	Congestive Heart Failure
CI	Confidence Interval
CONSORT	Consolidated Standards for Reporting Trials
CPT	Current Procedural Terminology
Cr	Creatinine
DM	Diabetes Mellitus
DVT	Deep Venous Thromboembolism
Dx	Diagnosis
EMR	Electronic Medical Records
ESC	European Society of Cardiology
GFR	Glomerular Filtration Rate
GI	Gastrointestinal
H2 Receptor	Histamine H2 Receptor
HAS-BLED	Hypertension, Abnormal Liver/Renal function, Stroke, Bleeding history or predisposition, Labile INR, Elderly (Age >65), Drugs-Alcohol usage
HbA1c	Hemoglobin A1C
HCPC	Healthcare Common Procedure Coding
hdPS	High-dimensional Propensity Score
HR	Hazard Ratio
ICD-9	International Classification of Diseases, Ninth Revision, Clinical Modification
ICH	Intracerebral Hemorrhage
INR	International Normalized Ratio
ITT	Intent-To-Treat
IRB	Institutional Review Board
ISF	Investigator Site File

LDL	Low Density Lipoprotein
LOS	Length of Stay
MDRD	Modification of Diet in Renal Disease
MI	Myocardial Infarction
NOAC	New Oral Anticoagulant
NSAID	Non-steroidal Anti-inflammatory Drug
NVAF	Non-valvular Atrial Fibrillation
PAD	Peripheral Artery Disease
PCI	Percutaneous Coronary Intervention
PE	Pulmonary Embolism
PGP	P-glycoprotein
PPI	Proton Pump Inhibitor
PPV	Positive Predictive Value
PS	Propensity Score
PTCA	Percutaneous Transluminal Coronary Angioplasty
PVD	Peripheral Vascular Disease
PY	Person-Year
RE-LY	Randomized Evaluation of Long-Term Anticoagulation Therapy
RR	Relative Risk
SAH	Subarachnoid Hemorrhage
SBP	Systolic Blood Pressure
SCr	Serum Creatinine
SD	Standard deviation
TIA	Transient Ischemic Attack
t.i.d.	ter in die (3 times a day)
US	United States
VTE	Venous Thromboembolism

#### 4. ABSTRACT

Name of company: Boehringer Ingelheim			
Name of finished medicinal product: Pradaxa® (Dabigatran etexilate), or warfarin			
Name of active ingredient: Dabigatran etexilate or warfarin			
Protocol date: 02 November 2016	Study number: 1160.219	Version/Revision: 1.0	Version/Revision date:
Title of study:	Association of select EMR-based covariates with oral anticoagulant medication selection Version and date: Version 1.0, 02 November 2016 		
Rationale and background:	A study of safety/effectiveness of dabigatran is being conducted in health insurer claims databases that may incompletely capture select variables representing covariates. This validation study seeks to ascertain a select set of covariates in electronic medical records (EMRs) linked to a subset of patients within the insurance claims data in order to assess the potential for unmeasured confounding in observational studies based on insurance claims databases only.		
Research question and objectives:	The research question is whether select patient characteristics that may be incompletely captured by insurance claims data differ between dabigatran and warfarin initiators. Objectives: 1) Descriptive: To identify select clinical covariates from electronic medical records that might be associated with initiation of oral anticoagulant medications (dabigatran or warfarin) in patients with NVAf at risk for stroke and are not usually well captured in the associated claims database. 2) Prediction Rule: To quantify the association between EMR-based clinical characteristics and patterns of insurance claims		

Name of company: Boehringer Ingelheim			
Name of finished medicinal product: Pradaxa® (Dabigatran etexilate), or warfarin			
Name of active ingredient: Dabigatran etexilate or warfarin			
Protocol date: 02 November 2016	Study number: 1160.219	Version/Revision: 1.0	Version/Revision date:
Research question and objectives:	3) Assess Balance: To assess the potential for unmeasured confounding in dabigatran vs warfarin comparative effectiveness and safety studies based on administrative claims databases		
Study design:	A validation study		
Population:	
Patients from an US health insurance database (electronic medical records) with a recorded diagnosis of atrial fibrillation without evidence of valvular etiology and at risk for stroke who initiate dabigatran or warfarin between October 2010 and December 2014 (This date range corresponds to the available matched cohort date range).
 
Inclusion criteria:
 
 
• A recorded diagnosis of atrial fibrillation.
 
• Initiation of anticoagulant medication (dabigatran or warfarin).
 
• At least 18 years of age on the date of anticoagulant initiation.
 
• CHA2DS2-VASc score ≥ 1
 
• Presence of electronic medical records (for the EMR-based subset)
 
 
Exclusion criteria:
 
 
• Patients with missing or ambiguous age or sex information.
 
• Patients with evidence of valvular disease.
 
• Patients with less than 12 months enrolment preceding the date of anticoagulant initiation.
 
• Patients with a dispensing of any oral anticoagulant during the 12 months preceding the date of anticoagulant initiation
 
• Patients with a nursing home stay during baseline
 
• Unmatched dabigatran/warfarin initiators
 
		

Name of company: Boehringer Ingelheim			
Name of finished medicinal product: Pradaxa® (Dabigatran etexilate), or warfarin			
Name of active ingredient: Dabigatran etexilate or warfarin			
Protocol date: 02 November 2016	Study number: 1160.219	Version/Revision: 1.0	Version/Revision date:
Variables:	
Patient characteristics derived from insurance claims (claims-based covariates)
 
This study will characterize patients initiating oral anticoagulant medications with respect to select characteristics, some of which might be reflected differently in claims data compared to electronic medical records prior to and including the date of initiation. These characteristics from EMR data are usually treated as covariates but will be considered outcomes in this validation study.
 
These characteristics include:
 
Primary Outcomes
 
 
• Obesity
 
• Smoking
 
• Alcohol consumption
 
• Abnormal renal function
 
• Bleeding history or predisposition
 
• Renal function (estimated GFR)
 
• Serum Creatinine
 
• Abnormal liver function
 
 
Secondary Outcomes
 
 
• Duration of atrial fibrillation
 
• History of adherence
 
• History/duration of hypertension
 
• Uncontrolled Hypertension (for HAS-BLED)
 
• History/duration of CHF
 
• Prior TIA
 
• Diabetes
 
• Hyperlipidemia
 
		

Name of company: Boehringer Ingelheim			
Name of finished medicinal product: Pradaxa® (Dabigatran etexilate), or warfarin			
Name of active ingredient: Dabigatran etexilate or warfarin			
Protocol date: 02 November 2016	Study number: 1160.219	Version/Revision: 1.0	Version/Revision date:
Variables:	
 
HAS-BLED Score
 
Use of antiplatelets or NSAIDs (needed for HAS-BLED)
 
		
Data sources:	This study will be conducted within MarketScan data linked to electronic medical records.		
Study size:	
Study cohort: approximately 15,000 dabigatran initiators PS-matched to 15,000 warfarin initiators
 
EMR-linked subset: approx. 5.5% of the study cohort.
		
Data analysis:	
 
Analyses will describe the presence in the claims data of each EMR-based clinical characteristic among initiators of dabigatran and initiators of warfarin.
 
A prediction algorithm to identify in the claims data each of the EMR-based clinical characteristic will be developed. The prediction algorithm will be estimated using a regression model that uses each of the EMR characteristic as the model outcome and all available claims-based covariates as predictors.
 
Strength of association between each EMR-based covariate and medication choice will guide quantitative assessments of potential confounding of the association between anticoagulant and clinical outcomes.
 
		
Milestones:	
Draft Protocol: September 2013
 
Final Protocol: November 2016
 
Draft Report: July 2017
 
Final Report: September 2017
		

## **5. AMENDMENTS AND UPDATES**

None.

## **6. MILESTONES**

Milestone	Planned Date
Contract	June 2012
Draft protocol	September 2013
Final protocol	November 2016
Start of data collection	15 November 2016
End of data collection	15 May 2017
First draft report	July 2017
Registration in the EU PAS register	November 2016
Final report of study results:	September 2017

## 7. RATIONALE AND BACKGROUND

A number of new oral anticoagulants are being developed and marketed to replace vitamin K antagonists, one of the most important drugs in modern medicine. [P11-11875] Unlike vitamin K antagonists, these new drugs do not require dose titration involving intensive therapeutic monitoring of prothrombin time to achieve target anticoagulation within a narrow therapeutic range. In Phase III studies, these drugs were found to be therapeutically advantageous or non-inferior over warfarin. In the coming years, as many as six new anticoagulants could be on the market and a lack of valid comparative evidence will hinder prescriber and payor decision-making.

Pharmacoepidemiologic studies based on large administrative claims databases are increasingly utilized for that purpose; however, these data are collected for reasons unrelated to research, and as a result, might not contain sufficient information on important confounders, such as body mass index, smoking, family history, or alcohol consumption, leading to residual confounding. Several approaches have been proposed to address the issue of unmeasured confounding, and internal validation studies, based on additional data obtained for a subset of participants in the main study population is one of them. Such studies offer specific advantages since they are more representative of the main study population and allow application of methods that do not require assumptions about the direction of confounding. [R13-2768]

This protocol is for a validation study conducted within a cohort of patients initiating dabigatran or warfarin during October 2010 – December 2014 time period and matched on propensity score (PS). The study will involve targeted data ascertainment from linked patients for enhanced covariate assessment via extraction from electronic medical records using existing electronic data including pre-defined variables, with the goal of describing the presence of covariates not typically present or insufficiently measured in claims data in dabigatran users as compared to users of warfarin and assessing the potential for confounding in the comparative safety research that will be undertaken in other phases of the study program.

## **8. RESEARCH QUESTION AND OBJECTIVES**

The objectives of this study are:

- 1) **Descriptive:** To identify select clinical covariates from electronic medical records that might be associated with initiation of oral anticoagulant medications (dabigatran or warfarin) in patients with NVAF at risk for stroke and are not usually well captured in the associated claims database.
- 2) **Prediction Rule:** To quantify the association between EMR-based clinical characteristics and patterns of insurance claims
- 3) **Assess Balance:** To assess the potential for unmeasured confounding in dabigatran vs warfarin comparative effectiveness and safety studies based on administrative claims databases

## 9. RESEARCH METHODS

### 9.1 STUDY DESIGN

This study represents a form of internal validation study that will involve selection of a patient sample, extraction of medical record data, and analyses that will have implications for potential confounding in comparative studies of dabigatran effect.

This study will be conducted within a cohort of NVAf patients at risk for stroke initiating dabigatran or warfarin during October 2010 – December 2014 time period identified in MarketScan research claims database based on Protocol 1160.207 (Sequential Expansion of Comparative Effectiveness of Oral Anticoagulants).

### 9.2 SETTING

The data source for this project will be MarketScan, a research claims database from commercial employer-sponsored health plans.

### 9.3 VARIABLES

#### 9.3.1 Exposures

The primary exposure is new initiation of warfarin or dabigatran. Initiators are defined as no anticoagulation with *any oral anticoagulant* in the 12 months before the index prescription. Comparison between these two groups of initiators will be made with respect to variables obtained from the EMR among patients who have been matched on the propensity score derived from insurance claims data.

#### 9.3.2 Outcomes

EMR-based clinical characteristics that are typically used as covariates will be treated as outcomes in this validation study. Unless otherwise noted, all of these outcomes will have an indicator for being recorded in EMR (Present, Y/N). Index date is the date of dabigatran or

warfarin initiation. All characteristics will be assessed prior and including the medication initiation date (index date). The characteristics presented in [Table 1](#) reflect likely availability in the EMR.

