**Table 1 Outcome definitions**

Outcome	Definition	Present	Categories if present
Primary			
Obesity	Calculated BMI >30 or recorded "obesity"	Y/N	Obese, not-obese based on note of obesity or recorded BMI>30.
Smoking	Any note on smoking	Y/N	Current & past combined and nonsmoker & not noted combined.
Alcohol consumption	Any note on alcohol use	Y/N	Alcohol use (any); No use
Abnormal renal function	Any note of: Dialysis, renal transplant Serum Creatinine >1.3 mg/dL	Y/N	
Bleeding history or predisposition	Any note of: Major bleeding requiring hospitalization or blood transfusion or causing a decrease in hemoglobin level of > 2 g/L	Y/N	
Renal function	Estimated GFR closest to index dispensing	Y/N	The value
Serum Creatinine	Closest to the index date	Y/N	The value
Abnormal liver function	Any note of: Liver disease, cirrhosis, Active hepatitis C Active hepatitis B Active hepatitis A AST/ALT >3X upper limit of normal Absence of any note would be considered as absence of the disease	Y/N	

[figure not shown]
Table 1 (cont'd) Outcome definitions

[figure not shown]
Outcome	Definition	Present	Categories if present
Secondary			
Duration of atrial fibrillation	Years/months prior to initiation of dabigatran/warfarin	Y/N	Number of months prior to index date for the earliest note
History of adherence	Any note of patient adherence/lack thereof in EMR	Y/N	Non-adherent Adherent
History/duration of hypertension	Any note of: Hypertension SBP >120 mmHg Hypertension drugs	Y/N	Number of months prior to index date for the earliest date
Uncontrolled Hypertension (for HASBLED)	SBP >160 mmHg using the most recent information prior to index date	Y/N	
History/duration of CHF	Any note of: CHF	Y/N	Number of months prior to index date for the earliest note
Prior TIA	Any note of TIA	Y/N	Also, number of months prior to index date if noted
Diabetes	Any note of: Diabetes Absence of any note of diabetes will be considered as absence of the disease	Y/N	
Hyperlipidemia	Any note of; Hyperlipidemia, dyslipidemia, LDL>130 mg/dl		
HAS Bled Score	As recorded (if recorded) or calculated from EMR data. [REDACTED]	Recorded/ calculated /none	The value
Use of antiplatelets or NSAIDs (needed for HASBLED)	Use of aspirin, clopidogrel, prasugrel, ticagrelor or NSADs (within 1 month or on the index date)	Y/N	
INR	Closest to the index date	Y/N	The value

[figure not shown]

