**Table 8 Association between claims-based covariates and EMR linkage.**

Claims-based covariate	Dabigatran initiators		Warfarin initiators	
	N=		N=	
	Linked	Not linked	Linked	Not linked
Proportion (N)				
Age				
Age category 18-35				
Age category 36-64				
Age category 65-74				
Age category 75+				
Sex				
...				

*Objective 1: Descriptive*

The analyses for this objective will occur within the subpopulation of individuals with linked EMR data and will focus on describing the EMR-based clinical characteristics for the dabigatran and warfarin initiators. This table will provide an evaluation of the association between the EMR clinical characteristics and initiation of dabigatran or warfarin. [REDACTED]

The prevalence of each category for categorical characteristics and the mean and standard deviation for continuous characteristics will be calculated (as shown in the example [Table 9](#)). This analysis will aid in identifying EMR characteristics that are unbalanced across exposure groups and are therefore potential unmeasured confounders after PS matching.

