**Table 9** **EMR clinical characteristics in matched dabigatran and warfarin initiators**

EMR clinical characteristic	Dabigatran initiators	Warfarin initiators
	N=	N=
[REDACTED]		
Smoking		
Alcohol consumption		
Obesity		
...		

[figure not shown]
Note: anticoagulant initiation [REDACTED] are based on claims data

We will seek to define variables derived from the EMR in a manner that reduces missingness. Accordingly, most variables will be defined as presence or non-presence in the EMR, which we will take as a proxy of being medically-recognized. For example, if smoking is noted in the medical record, it will be recorded as present, if it is not present, it will be assumed that the patient does not smoke. We will also evaluate the patterns of missing data in the EMR clinical characteristics.

Objective 2: Prediction Rule

[figure not shown]
Within the EMR linked subpopulation, a prediction model will be developed [REDACTED] with particular focus on covariates that are found to represent potentially important unmeasured confounding in the primary analysis. Specifically, a logistic regression model (potentially a multinomial logistic regression, depending on the number of categories for the EMR characteristic) will be estimated [REDACTED] that uses the EMR covariate as the model outcome and all available claims-based covariates as predictors. [REDACTED]

For [REDACTED] continuous EMR-based characteristic, a linear regression model will be estimated. Coefficients from these models will be reported as well as prediction accuracy, defined by the R2 statistic.

*Objective 3: Potential Unmeasured Confounding Assessment*

To assess the potential for confounding, we will conduct a series of logistic regression analyses that predict exposure (dabigatran versus warfarin) from covariates.

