## **9.11 SUBJECTS**

### **9.11.1 Study group**

The main cohort will consist of patients with NVAf at risk for stroke initiating warfarin and dabigatran, from October 2010 through December 2014.

Inclusion criteria:

- Initiation of an oral anticoagulant is defined by a dispensing of an anticoagulant medication (warfarin or dabigatran) in the source data, with no dispensing of any oral anticoagulant in the prior 12 months. The date of that dispensing will be defined as the index date for that initiation.
- At least one ICD-9 diagnosis code of 427.31 (atrial fibrillation) at any time prior to and including the index date
- At least 12 months (365 days) continuous enrollment, defined as  $\leq 32$  days enrollment gap using enrollment and disenrollment dates, preceding the index date
- 18 years of age and older at index date
- CHA2DS2-VASc score  $\geq 1$

Exclusion criteria:

- Patients with a nursing home stay during baseline
- Patients with missing or ambiguous age or sex information.
- Patients with a dispensing of any oral anticoagulant during the 12 months preceding and including the index date
- Patients with documented evidence of valvular disease defined as at least 1 inpatient or outpatient ICD-9 Dx code of [\[R11-4334\]](#)  
394.x (diseases of mitral valve)  
395.x (diseases of aortic valve)  
396.x (diseases of mitral and aortic valve)  
397.x (diseases of other endocardial structures)  
398.9x (other and unspecified rheumatic heart diseases)  
V42.2 (heart valve replaced by transplant)  
V43.3 (heart valve replaced by a mechanical device/prosthesis)  
OR  
ICD-9 procedure code 35.1x (open heart valvuloplasty without replacement), 35.2x (replacement of heart valve) [\[R03-1232\]](#)  
OR  
one of the following CPT codes:  
33660-33665 (atrioventricular valve repair)  
33400-33403 (aortic valve valvuloplasty)  
33420-33430 (mitral valve repair/valvuloplasty/replacement)  
33460 (valvectomy, tricuspid valve, with cardiopulmonary bypass)  
33463-33468 (tricuspid valve repair/valvuloplasty/replacement)  
33475 (replacement, pulmonary valve)

33496 (prosthetic valve dysfunction repair)  
0257T (implantation of catheter-delivered prosthetic aortic heart valve; open thoracic approach)  
0258T (transthoracic cardiac exposure for catheter-delivered aortic valve replacement; without cardiopulmonary bypass)  
0259T (transthoracic cardiac exposure for catheter-delivered aortic valve replacement; with cardiopulmonary bypass)  

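### INR up to and including the first dispensing day can be a consequence of choosing warfarin, so an INR imbalance could be misread as unmeasured confounding

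*Combined protocol and SAP*

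**What the plan says.** INR is the last row under Secondary in Table 1. It is defined as "Closest to the index date", with a yes/no entry for being present and the value itself. The row gives no look-back limit and no condition that the sample precede the first dose.

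Section 9.3.2 supplies the general rules. On timing: "All characteristics will be assessed prior and including the medication initiation date (index date"). On recording: "Unless otherwise noted, all of these outcomes will have an indicator for being recorded in EMR (Present, Y/N"). So whether an INR was recorded is a variable in its own right, alongside its level.

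Section 9.11.1 fixes the index date from claims: "The date of that dispensing will be defined as the index date for that initiation". Section 7 says of the newer anticoagulants, in contrast to vitamin K antagonists, that "these new drugs do not require dose titration involving intensive therapeutic monitoring of prothrombin time".

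On use, section 9.7.1 says under Objective 1: "This analysis will aid in identifying EMR characteristics that are unbalanced across exposure groups and are therefore potential unmeasured confounders after PS matching". Under Objective 3, "we will conduct a series of logistic regression analyses that predict exposure (dabigatran versus warfarin) from covariates".

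INR does not appear in the secondary outcome lists of section 9.3.2.2 or the abstract.

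**The concern.** A confounder has to precede the treatment choice or be independent of it. INR near the start of warfarin may be neither, for two separate reasons.

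- **The recording flag.** If an INR is ordered because warfarin has been chosen, the test falls on or shortly before the dispensing date, inside the window. The flag is then a result of the choice.
- **The value.** If warfarin was started before the first dispensing claim, for example during a hospital stay, the INR nearest the index date may already reflect the drug. Whether and how often this happens in the linked data is an assumption; the documents do not say.

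The study exists to judge whether claims-based comparisons of dabigatran and warfarin suffer from unmeasured confounding. An INR imbalance that arises in either way says nothing about that, but under the stated reading it could count as evidence for it. If INR entered a multivariable exposure model, it could also distort the coefficients of genuine baseline covariates.

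**Working it through.** **Reading the sections together**

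1. The window ends on the index day (9.3.2), and the index day is a dispensing (9.11.1). It is not the date of the treatment decision and need not be the date of the first dose. Tests between decision and dispensing therefore fall inside the window.
2. Taking the nearest value (Table 1) favours exactly those tests over older ones.
3. Section 7 ties this kind of monitoring to one of the two drugs.
4. Imbalance is the only visible criterion for a potential confounder (9.7.1). Section 9.12 says that a relevant characteristic must also predict study outcomes, but section 9.9 says that this association is not assessed here. No visible step would screen out an imbalance caused by the choice of drug.

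**Sample size on which an imbalance would be judged**

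Section 9.5: 20,000 × 0.055 = 1,100 linked patients per group, which reproduces the stated figure. The abstract's 15,000 per group gives 15,000 × 0.055 = 825.

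**Illustration for the recording flag (assumed inputs)**

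Let p0 be the share in both groups with an INR recorded for unrelated reasons. Let f be the share of the remaining warfarin initiators who are tested only because warfarin was chosen. Then

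p1 = p0 + (1 − p0) × f

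d = (p1 − p0) / √{[p0(1 − p0) + p1(1 − p1)] / 2}

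Example with p0 = 0.20 and f = 0.10: p1 = 0.20 + 0.80 × 0.10 = 0.28, and d = 0.08 / √[(0.16 + 0.2016) / 2] = 0.188.

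Power is for a two-sided 5% test of two proportions (normal approximation). The 5% level is also an assumption.

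| f | p0 | p1 | d | Power, 1,100 per group | Power, 825 per group |
|---|---|---|---|---|---|
| 2% | 10% | 11.8% | 0.06 | 27% | 22% |
| 2% | 20% | 21.6% | 0.04 | 15% | 12% |
| 2% | 40% | 41.2% | 0.02 | 8% | 7% |
| 5% | 10% | 14.5% | 0.14 | 90% | 80% |
| 5% | 20% | 24.0% | 0.10 | 62% | 50% |
| 5% | 40% | 43.0% | 0.06 | 30% | 24% |
| 10% | 10% | 19.0% | 0.26 | >99% | >99% |
| 10% | 20% | 28.0% | 0.19 | 99% | 97% |
| 10% | 40% | 46.0% | 0.12 | 81% | 69% |
| 20% | 10% | 28.0% | 0.47 | >99% | >99% |
| 20% | 20% | 36.0% | 0.36 | >99% | >99% |
| 20% | 40% | 52.0% | 0.24 | >99% | >99% |

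**Illustration for the value (assumed inputs)**

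Assume an untreated INR with mean 1.1 and SD 0.2, and a mean of 1.8 (same SD) in patients already on warfarin, a shift of 0.7. Let p be the share of such patients among warfarin initiators with an INR value.

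Mean difference = 0.7p; warfarin-group variance = 0.04 + p(1 − p) × 0.49; d = 0.7p / √[(0.04 + warfarin-group variance) / 2].

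- p = 5%: 0.035 / √[(0.04 + 0.0633) / 2] = 0.15
- p = 10%: 0.07 / √[(0.04 + 0.0841) / 2] = 0.28
- p = 20%: 0.14 / √[(0.04 + 0.1184) / 2] = 0.50

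In both illustrations the two groups have no true baseline difference. The result depends almost wholly on f or p, and the documents give neither.

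**The case against.** The other side has four good points.

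- **A pre-dose value is a genuine baseline measurement.** Post-index values are excluded, and section 9.3.1 sets a new-user rule: "Initiators are defined as no anticoagulation with *any oral anticoagulant* in the 12 months before the index prescription". Warfarin cannot change an INR drawn before the first dose, and that INR may reflect liver function or clotting status. This stands. A test ordered because of the choice of drug affects the flag, not the pre-dose value. The new-user rule does not settle the matter, though: section 9.11.1 applies it to dispensings, so it would not detect a start that produced no dispensing claim, and it does nothing about tests ordered in anticipation of warfarin.
- **INR's role is unclear.** It is in Table 1 but not in the outcome lists. The visible rows of Table 9 do not name it and end in an ellipsis, and parts of 9.7.1 are redacted. This stands: it cannot be shown that INR enters Table 9 or the Objective 3 models. Nor does the visible text exclude it.
- **The plan's wording is cautious.** It speaks of potential confounders and shows no numerical threshold. This also stands, so a misleading label is a possibility and not a certainty.
- **INR may be wanted for HAS-BLED.** Table 2 includes a labile-INR item, and Table 1 allows the score to be calculated from EMR data. Removing INR altogether could therefore cost something.

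A reader might infer that INR will be among the largest imbalances and that the study will overstate unmeasured confounding. The documents do not support that. They give no testing shares, no share of starts before the index dispensing, and no statement that the linked EMR holds inpatient laboratory results.

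**Conclusion.** The concern holds in a limited form. As written, the window and the recording flag allow a consequence of choosing warfarin to be presented as a possible unmeasured confounder, and no visible step separates the two. The case is strongest for the flag, because it follows from the protocol's own statement about monitoring. For the value it applies only to patients who started before the first dispensing claim.

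The size is unknown. Under the assumptions shown, the flag's imbalance would be likely to show if about 10% or more of otherwise untested warfarin initiators were tested because of the drug (power 81% or more at 1,100 per group, 69% or more at 825). It would probably go unnoticed at 2%. The affected item is one secondary row whose role the plan does not state consistently. This is an inexpensive improvement to the plan and does not call the study design into question.

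**What to change.** 1. Leave the INR recording flag out of the confounder interpretation in Objective 1 and out of the exposure models in Objective 3. Report INR testing by group descriptively, with a note that it may result from the choice of drug.
2. If the INR value is kept, restrict it to values dated before the index date and before any EMR record of oral anticoagulant administration.
3. State separately whether, and from which measurements, INR is used for the labile-INR item of HAS-BLED.
4. Reconcile Table 1 with section 9.3.2.2 and the abstract, so that INR is either a listed secondary outcome or not one.

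The cost is wording, a little more analysis work and the loss of some INR values. No sample-size figure changes.
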